2.1.1 Feasibility of Intervention Measure

The FIM is employed to evaluate the feasibility of an implementation strategy. This four-item measure assesses perceived intervention feasibility. The items are measured on a five-point rating scale (1= $\frac{\text{CCI}}{\text{CCI}}$, 2= $\frac{\text{CCI}}{\text{CCI}}$ 3= $\frac{\text{CCI}}{\text{CCI}}$, 4= $\frac{\text{CCI}}{\text{CCI}}$ and 5= $\frac{\text{CCI}}{\text{CCI}}$. The FIM was validated with other implementation outcome measures. Higher scores indicate greater feasibility. There are no reverse-scored items on the FIM, and the mean score for feasibility of the

2.1.2 Acceptability of Intervention Measure

intervention is calculated by averaging the responses from four items.

The AIM is employed to evaluate the acceptability of an implementation strategy. This four-item measure assesses perceived intervention acceptability. The items are measured on a five-point rating scale (1= $\frac{\text{CCI}}{\text{CCI}}$, 2= $\frac{\text{CCI}}{\text{CCI}}$ 3= $\frac{\text{CCI}}{\text{CCI}}$, 4= $\frac{\text{CCI}}{\text{CCI}}$ and 5= $\frac{\text{CCI}}{\text{CCI}}$). The AIM was validated with a suite of implementation outcome measures. Higher scores indicate greater acceptability. There are no reverse-scored items on the AIM, and the mean score for acceptability of the intervention is calculated by averaging the responses from four items.

2.1.3 HIV Care Provider/Clinical Staff Additional Questionnaire

The tailored HIV care provider/clinical staff questionnaire was developed specifically for this study and contains items regarding the provider's practice and experience, as well as their attitudes, expectations, and concerns regarding the use of CABENUVA/long-acting injectable administered by ICs/ASAs. The baseline HIV care provider/clinical staff questionnaire has 38 items (including the FIM and AIM) using several different response scales.

2.1.4 Expert Panel Additional Questionnaire

The tailored Expert Panel questionnaire items were developed specifically for this study and contain items regarding the Expert Panel's preferences and assessment for CABENUVA administration. The baseline questionnaire has 18 items using several different response scales.

3 Statistical Methods

This SAP has been developed to guide the analyses for the data collected and assumes that all data will be collected in adherence to the protocol developed by GSK/ViiV. There are two analysis populations discussed in this SAP: (1) all responding HIV care providers/clinical staff who complete any portion of any questionnaire at any point in the study and (2) all responding members of the Expert Panel comprised of key IC/ASA staff members involved in decision making and/or oversee daily operations at the IC/ASA, selected HIV care providers, and ViiV members who complete any portion of any questionnaire at any point in the study. As the data are analyzed, some deviation from expectations may occur. In instances where these deviations would make the proposed analyses inappropriate, modifications to the analysis

A Phase 4, Open-label, Single-arm Study to Optimize Implementation of CABENUVA for the Treatment of HIV-1, for Administration in US Community-based Infusion Centers or Alternate Sites of Administration

plan, along with justifications for these changes, will be made and noted in the final report. Given the small sample size of HIV care providers/clinical staff and the Expert Panel, the planned analyses will be descriptive.

Continuous and interval-like variables will be summarized using descriptive statistics (e.g., n, mean, standard deviation [SD], median, minimum, maximum, first and third quartiles, and 95% confidence intervals [CI]). Data in tables will be tabulated relative to the source data. Mean, median, quartiles, and percentages will be tabulated to one more decimal place than the source data; minimum/maximum values will have the same decimal places as source data; percentages will be rounded to one decimal place after calculation. SD and CIs will be tabulated to two more decimal places than the source data. Categorical variables will be reported as frequency counts, the percentage of HIV care providers/clinical staff and Expert Panel in corresponding categories, and 95% CIs.

Subgroup analysis will be performed to evaluate the effect of contextual factors on the variability of responses to feasibility, and acceptability. These factors will include, but are not limited to, affiliation for HIV care providers. Once specified these will be added to this SAP. No subgroup analyses will be performed for the Expert Panel due to insufficient sample size.

For the analyses of the proportion of HIV care providers/clinical staff and Expert Panel members responding agree or completely agree on all FIM items, this will include the HIV care providers/clinical staff and Expert Panel members who select response option 4 CCI or 5 CCI or 5 CCI or 6 for all four FIM items at a given time point, out of all HIV care providers/clinical staff and Expert Panel members who completed all four FIM items at that respective timepoint. The same definition applies to the analogous analysis for the AIM.

Table shells for analyses of HIV care providers/clinical staff can be found in Section 6, and for the Expert Panel can be found in Section 7.

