## 2.2. Rationale

This post-approval, Phase 4 study will use an Expert Panel consisting of selected HIV care providers that may refer their PLWHIV to an IC/ASA, key IC/ASA staff members

involved in decision making and/or oversight of daily operations and ViiV Healthcare (VHC) to collaboratively develop an implementation blueprint and a plan of treatment (POT) to establish best practices and standard operating procedures for the administration of CABENUVA at ICs/ASAs (see Section 5.1 for full descriptions of the blueprint and POT). The blueprint will be used to guide the development and/or refinement of the POT which will be reviewed prior to the HIV care provider's first patient with HIV-1 enrolled in the study at the IC/ASA.

Implementation science methodology will be used to assess the acceptability and feasibility of an IC/ASA for the delivery of CABENUVA IM injections. In this study, the intervention is the process of using an infusion center as the location to receive the CABENUVA IM injections. The acceptability and feasibility of the IC/ASA to deliver CABENUVA IM injections, will be assessed from the perspectives of the participants, HIV care providers/clinical staff and IC/ASA staff.

The intention of this post-approval study is to develop, evaluate and scale-up an implementation blueprint for IM administration of CABENUVA for HIV-1 treatment at ICs/ASAs. The study has two main components. The first component is to conduct a formative evaluation of the feasibility and acceptability of the IC/ASA model by participants, IC/ASA staff and HIV providers and the development of the implementation blueprint. The second component involves a scale-up of the implementation blueprint across all ICs/ASAs in this study.

An Expert Panel will meet to generate an implementation blueprint to guide successful implementation prior to the first participant first visit (FPFV). The blueprint will be optimized over the first 6 months and will be used as a foundation for the enrolment of the remaining participants. The Expert Panel will complete all assessments in Q4 2022. The optimized blueprint will be reviewed and potentially revised by key IC/ASA staff members involved in decision making and overseeing daily operations at the IC/ASA.

Participants enrolled in the study will receive commercially available CABENUVA via prescription from their HIV care provider. Participants will be monitored according to usual standard care at their physician's discretion.

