	Proportion of IC/ASA staff that agree or completely agree (a score of 4 or higher) across all items on the AIM prior to Month 1, at Month 3, and Month 8
	Change of HIV care providers/clinical staff over time in the AIM at Month 4 and Month 8
	Change of participants and IC/ASA staff respectively over time in the AIM at Month 3, and Month 8
	Summary of other quantitative questionnaires assessed with HIV care providers/clinical staff at Month 1, Month 4 and Month 8
	Summary of other quantitative questionnaires assessed at Month 1, Month 3, and Month 8 with participants
	Summary of other quantitative questionnaires assessed prior to Month 1, at Month 3 and Month 8 with IC/ASA staff
	Qualitative interviews assessed at Month 8 with participants, HIV care

Objectives	Endpoints
	providers/clinical staff and IC/ASA staff
To evaluate feasibility, acceptability and the process of CABENUVA administration at infusion centers from the Expert Panel	Proportion of Expert Panel that agree or completely agree (a score of 4 or higher) across all items on the FIM and AIM respectively prior to FPFV, and at Month 3 and Month 6
	Change of Expert Panel over time in FIM and AIM respectively through Month 6
	Summary of other quantitative questionnaires assessed with Expert Panel prior to FPFV, and at Month 3 and Month 6
	Qualitative interviews assessed with Expert Panel prior to FPFV and at Month 6
To evaluate perceptions, facilitators, and barriers/concerns by participants, HIV care providers/clinical staff, and IC/ASA staff	Summary of participant other quantitative questionnaires at Month 1, Month 3 and Month 8
	Summary of IC/ASA staff other quantitative questionnaires prior to Month 1, at Month 3, and Month 8
	Summary of HIV care provider/clinical staff other quantitative questionnaires at Month 1, Month 4, and Month 8
	Qualitative interviews assessed at Month 8 with HIV care providers/clinical staff, participants and IC/ASA staff
To assess the preference of participants on the location to receive CABENUVA	Summary of preference on the location to receive CABENUVA at Month 1, Month 3, and Month 8 assessed by participant other quantitative questionnaires
	Qualitative interviews assessed at Month 8 with participants

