## 5.1.1. Expert Panel

The Expert Panel (approximately 10 members) will convene prior to any participant enrolment and will develop a CABENUVA implementation blueprint and an IC POT for the study. The pre-determined panel will be comprised of key IC/ASA staff members involved in decision making and/or overseeing daily operations at the IC/ASA, selected HIV care providers and VHC. VHC will provide oversight, and participate on the Expert Panel, when appropriate to ensure critical components of the process are addressed and that the blueprint is complying with the protocol, and the delivery of the study objectives and endpoints. IC/ASA Staff and HIV care provider membership of this panel will be chosen after completion of feasibility, and members will be asked to remain on the panel for the duration of the Expert Panel.

Prior to any participant enrollment in the study, the Expert Panel members will participate in a brief baseline qualitative interview and a meeting to design the blueprint, which will provide guidance to any IC/ASA about the overall process and implementation strategies to support CABENUVA initiation and continuation injections and will be used for the development and/or refinement of the POT. Templated analysis will occur for rapid coding both instream during the interviews as well as afterwards, if necessary, to capture additional information. Data from all stakeholder interviews will be summarized for top level key constructs noted across interviews.

At the Expert Panel first meeting, the qualitative interview data will be discussed, elements for the blueprint that will be used to develop the IC/ASA POT will be identified. This blueprint and POT will direct the entire spectrum of users (participants, HIV care providers, IC/ASA staff) on processes including clinical procedures and facilitative communication. This process will follow an evidence-based qualitative improvement process (e.g., identifying potential barriers to implementation, generating a plan to address it, and ultimately testing through implementation) paired with a nominal

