Perceptions,	HIV Care Providers/	Qualitative Interview	M8
Facilitators, and Barriers/Concerns,	Clinical Staff	Other quantitative questionnaires	M1, M4, M8
	Participants	Qualitative Interview	M8
		Other quantitative questionnaires	M1, M3, M8
	IC/ASA Staff	Qualitative Interview	M8
		Other quantitative questionnaires	Prior to M1, M3, M8
Preferences	Participants	Qualitative Interview	M8
		Other quantitative questionnaires	M1, M3, M8
Advantages and Disadvantages	HIV Care Providers/ Clinical Staff	Qualitative Interview	M8
		Other quantitative questionnaires	M1, M4, M8
	Participants	Qualitative Interview	M8
		Other quantitative questionnaires	M1, M3, M8
Acceptability of	HIV Care Providers/ Clinical Staff	Qualitative Interview	M8
receiving and referring patients		Other quantitative questionnaires	M1, M4, M8
	Participants	Qualitative Interview	M8
		Other quantitative questionnaires	M1, M3, M8
Usefulness of the blueprint and POT	HIV Care Providers/	Qualitative Interview	M8
	Clinical Staff	Other quantitative questionnaires	M4, M8
	IC/ASA Staff	Qualitative Interview	M8
		Other quantitative questionnaires	Prior to M1, M3, M8
Overall opinion of receiving and administering the injections at an IC	HIV Care Providers/ Clinical Staff	Qualitative Interview	M8
		Other quantitative questionnaires	M1, M4, M8
	Participants	Qualitative Interview	M8
		Other quantitative questionnaires	M1, M3, M8
	IC/ASA Staff	Qualitative Interview	M8
		Other quantitative questionnaires	Prior to M1, M3, M8

Abbreviations: AIM: Acceptability of Intervention Measure; ASA: Alternate Sites for Administration; FIM: Feasibility of Intervention Measure; FPFV = First participant first visit, IC = Infusion Center; M: Month \*Expert Panel includes selected HIV Care Providers and Key IC Staff

Only HIV care providers/clinical staff that had patients enrolled into the study will be included in assessments post Baseline/Month 1.

<sup>†The Expert Panel will meet as required over the first 6 months to discuss any iterations that are needed to refine and optimize the blueprint.

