#### **Participants**

Baseline/Month 1 is defined as the date when a participant signs ICF and completes Baseline/Month 1 protocol procedures prior to receiving the first study related CABENUVA injections at the IC/ASA

All additional study visits, including those where questionnaires and/or interviews are administered at Months 3 and 8 will be anchored off of each participants Month 1 visit, so it will reflect the Months on study, regardless of what dosing regimen the participant is on (e.g., monthly or every 2 monthly) and regardless of whether they have missed any injections and received oral bridging.

Procedure 	Baseline/			Treatme	ent Period (	Months)			- E.D. 	Notes
Flocedule.	Month 1 	2	3	4	5	6	7	8	E.D.	Notes
Participant	X		Х					X	Х	At Month 1, Questionnaires should be completed after signing the ICF and before receiving CABENUVA IM injections or within 14 days following the Month 1 visit.
Questionnaires									A	Questionnaires should be completed before receiving CABENUVA IM injections or $\pm$ 14 days following the last visit.
Participant Interviews								Х	Х	Interviews will be completed at the participants last study Visit: Month 8 or early withdrawal visit. Interviews can be completed 2 weeks before or 2 weeks following the last visit.
•										Interviews should be completed before receiving CABENUVA IM injections if interviews are completed the day the injections are administered.

**Expert Panel**: will consist of key IC/ASA staff members involved in decision making and/or oversee daily operations at the IC/ASA, selected HIV care providers that may refer PLWHIV, and ViiV Healthcare (VHC). Panel members will meet prior to Baseline/Month 1 to design the Blueprint (Section 5.1.1)

Baseline/Month 1 is defined as the date when a participant signs ICF, completes protocol procedures and receives the first study related CABENUVA injections at any infusion center.

Month 3 and Month 6 assessments are to be completed after approximately 10 participants (across all ICs/ASA) have completed their Month 3 and Month 6 study visits at any IC/ASA site

Expert Panel X	X (Prior to					FIM, AIM (FIM and AIM also completed prior to FPFV at the Baseline/Month 1 visit)
F	Month 1)	X		Х		Meetings will be held as required over the first 6 months to discuss any iterations that are needed to refine and optimize the blueprint.
Questionnaires N	Month 1)	^		^		months to disc

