This is a Phase 4, single arm, open-label, multi-center study examining the administration of CABENUVA IM in IC/ASAs in the United States. This study is being conducted following Food and Drug Administration (FDA) approval and commercial availability of CABENUVA. Eligible and consenting participants will be followed for eight months to evaluate an implementation blueprint for IM administration of CABENUVA for HIV-1 treatment at ICs/ASAs. The total duration for study participants is approximately eight months from the time of enrollment and receipt of the first administration of CABENUVA IM injections at the ICs/ASA.

Relevant to this SAP, approximately 20 HIV care providers/clinical staff who refer their patients living with HIV to a study ICs/ASA to receive CABENUVA will be asked to complete questionnaires per the Schedule of Activities (SoA, see ANNEX 1 in protocol) after the HIV care provider's first referred patient is enrolled into the study. This study also has an Expert Panel, consisting of approximately 10 members, which will consist of key ICs/ASA staff members involved in decision making and/or oversee daily operations at the ICs/ASA, selected HIV care providers that may refer PLWHIV, and ViiV. Panel members will meet prior to Baseline/Month 1 to design the Blueprint.

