The HIV care provider/clinical staff questionnaire consists of two validated instruments and tailored items written for this study. The validated instruments are the FIM and AIM, described below. The tailored items ask HIV care providers/clinical staff about several topics including, but not limited to, their practice, experience, and views on the CABENUVA / long-acting injectable model, as well as using ICs/ASAs to implement that model. The Expert Panel questionnaire also consists of the FIM and AIM and tailored items. Two different versions of the FIM and AIM will be used for the Expert Panel: one for HIV care providers/clinical staff and one for IC/ASA staff. Across FIM and AIM versions, the stem of each item has slightly different wording, reflecting the different roles of HIV care providers/clinical staff and IC/ASA staff. Response options are the same across versions. Due to the small numbers on the Expert Panel, the FIM and AIM will be summarized in all tables together, though the differences in the wording for underlying groups, due to their different roles, should be noted. The tailored items will ask the Expert Panel about the specifics of the implementation of the study.

A feasibility composite score for HIV care providers/clinical staff and Expert Panel, to be determined, will be added to this SAP. The exact components of the feasibility composite score will be informed by the Expert Panel process to ensure it matches the critical variables identified by all members of the panel.

Table B. Questionnaire Administration for HIV Care Provider/Clinical Staff and Expert Panel

Questionnaire	Baseline	Month 3	Month 4	Month 6	Month 8
HIV Care Provider Tailored Items, HIV Care Provider/ Clinical Staff	Х		Х		х*
Feasibility of Intervention Measure, HIV Care Provider/ Clinical Staff	Х		Х		х
Acceptability of Intervention Measure, HIV Care Provider/ Clinical Staff	х		х		х
Feasibility of Intervention Measure, Expert Panel	Х	Х		Х	

Questionnaire	Baseline	Month 3	Month 4	Month 6	Month 8
Acceptability of Intervention Measure, Expert Panel	Х	Х		Х	

Abbreviation: HIV = human immunodeficiency virus

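### The Expert Panel analysis population admits ViiV members, who have no applicable FIM/AIM form and a stake in the program, and pools any responses they give into a secondary endpoint

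*SAP*

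**What the plan says.** The secondary endpoint in Protocol Section 3 is the "Proportion of Expert Panel that agree or completely agree (a score of 4 or higher) across all items on the FIM and AIM respectively", assessed before the first participant's first visit and at Months 3 and 6, together with change over time.

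The SAP for HIV care providers and the Expert Panel defines two analysis populations in Section 3. The second is the responding panel: key IC/ASA staff, "selected HIV care providers, and ViiV members who complete any portion of any questionnaire at any point in the study". The same section takes the endorsement proportion over panel members who completed all four items, and rules out panel subgroup analyses because the sample is too small. Section 2.1 says that two FIM/AIM versions will be used for the panel, "one for HIV care providers/clinical staff and one for IC/ASA staff", and that both will be summarized together in all tables.

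The protocol describes the panel in several places. Sections 2.2 and 5.1.1 and Annex 1 name VHC. Section 5.1.1 reads "selected HIV care providers and VHC. VHC will provide oversight, and participate on the Expert Panel, when appropriate". The footnote to Table 1 (Section 5.1.2), which is attached to the panel's feasibility and acceptability rows, reads "Expert Panel includes selected HIV Care Providers and Key IC Staff" and does not mention VHC.

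**The concern.** Belonging to the panel and being an assessed stakeholder are different things. VHC's stated task on the panel is to see that the process covers what it must and that the blueprint complies with the protocol. No text says that VHC rates feasibility or acceptability. The SAP population rule nevertheless admits ViiV members as respondents.

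Two things follow if any of them answer. First, the items do not fit. One version asks about the respondent's own clinic or practice, the other about the respondent's own infusion center, and the documents give a ViiV member neither. Second, ViiV has an interest in the answer: CABENUVA is listed as its trademark, and Protocol Section 2.2 has VHC helping to develop the blueprint. The expected direction is toward agreement. In a panel of about 10, a few such responses could change the reported proportion visibly, and because the tables pool everyone, a reader could not see it.

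**Working it through.** The plan gives no figure to reproduce on this point, so the check is a comparison of the texts followed by an illustration of size.

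**Who is on the panel, and who is assessed**

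| Place | VHC/ViiV named? | What it governs |
|---|---|---|
| Protocol 2.2 | Yes | Panel membership |
| Protocol 5.1.1 | Yes, with oversight | Panel membership and role |
| Protocol Annex 1, text above the panel questionnaire rows | Yes | Panel membership, next to the assessments |
| Protocol Table 1 footnote | No | Panel rows for FIM, AIM and other assessments |
| Provider/Expert Panel SAP, Sections 1 and 2 | Yes | Panel membership |
| Provider/Expert Panel SAP, Section 3 | Yes, as respondents | Analysis population |
| Same SAP, Section 2.1 and notes to the panel FIM/AIM tables | No | FIM/AIM versions and item wording |
| Same SAP, Tables 8.1 to 8.3.2 | No | Tailored items: HIV care providers and IC staff |

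ViiV is therefore on the panel in most places, is a respondent in the SAP population rule, and has no questionnaire anywhere.

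**Size of the effect**

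Inputs: panel size of about 10 (Protocol 5.1.1), taken as exactly 10 with complete items. The number of ViiV respondents, k, is not given; I assume 1 to 3, all endorsing every item. Let m = 10 − k be the other members and y the number of them who endorse.

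- With ViiV: (y + k)/10
- Without ViiV: y/m
- Shift = (y + k)/10 − y/m = (k/10) × (1 − y/m)

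Holding the pooled result at 8/10 = 80.0%, with exact (Clopper-Pearson) 95% intervals chosen for the illustration:

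| k | With ViiV | Without ViiV | Shift (points) |
|---|---|---|---|
| 1 | 8/10 = 80.0% (44.4 to 97.5) | 7/9 = 77.8% (40.0 to 97.2) | 2.2 |
| 2 | 8/10 = 80.0% | 6/8 = 75.0% (34.9 to 96.8) | 5.0 |
| 3 | 8/10 = 80.0% | 5/7 = 71.4% (29.0 to 96.3) | 8.6 |

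With about half of the others endorsing:

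| k | With ViiV | Without ViiV | Shift (points) |
|---|---|---|---|
| 1 | 5/10 = 50.0% | 4/9 = 44.4% | 5.6 |
| 2 | 6/10 = 60.0% | 4/8 = 50.0% | 10.0 |
| 3 | 6/10 = 60.0% | 3/7 = 42.9% | 17.1 |

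If all the others endorse, 1 − y/m = 0 and the shift is zero for any k.

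**The case against.** A reader might infer that the SAP contradicts the protocol's definition of the panel. It does not. Protocol Sections 2.2 and 5.1.1 and Annex 1 all place VHC on the panel, and Annex 1 does so directly above the panel's questionnaire rows. Only the Table 1 footnote omits VHC, and its verb, to include, does not exclude anyone. This is an unresolved inconsistency within the protocol, and the SAP follows the broader version.

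A reader might also take each ViiV respondent to be worth 10 percentage points. That is the respondent's share of a denominator of 10. The shift equals it only when none of the other members endorse; in the 80% example, one ViiV member moves the result by 2.2 points. Nor does 80% mark a threshold here. It appears in Protocol Section 6.1 for the participant primary endpoint, and no success criterion is set for the panel.

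Other parts of the opposing case also stand. Nothing shows that a ViiV member was given or completed a questionnaire, so Section 3 of the SAP may only be restating membership. The documents say ViiV members, so calling them sponsor employees is an inference. Bias toward agreement is expected but not demonstrated. The panel's providers and IC/ASA staff also helped write the blueprint they rate, so removing ViiV does not leave wholly independent raters.

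This argues for modest wording but does not remove the point. Providers and center staff hold the roles that the items ask about and are among the perspectives that Protocol Section 2.2 says will be assessed. ViiV members are neither.

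**Conclusion.** The point holds in a limited form. The SAP's population rule admits respondents who have no applicable form and an interest in the result, and the planned tables would not show their contribution. The protocol does not settle whether ViiV members are respondents.

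Under the assumptions above (10 complete responders, 1 to 3 from ViiV, all endorsing), the pooled proportion is higher by 0 to about 17 points across the scenarios tried, and by 2.2 to 8.6 points when the pooled result is 80%. If no ViiV member answered, there is no effect. The intervals are so wide that no firm conclusion rests on this proportion either way. The panel analysis is descriptive by the SAP's own statement, and the primary endpoint, participant FIM at Month 8, is untouched.

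**What to change.** In Section 3 of the provider/Expert Panel SAP, report the panel FIM and AIM proportions, and their change over time, for HIV care providers and IC/ASA staff only. List any ViiV responses separately, or show each result with and without them, and state how many ViiV members answered and on which version of the form. If none did, say so and drop ViiV from the population definition.

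Reconcile Protocol Section 5.1.1, the Table 1 footnote, Annex 1 and SAP Section 3 on whether ViiV members are respondents or only panel members. Changing the SAP alone would leave an endpoint defined on a panel that still includes VHC.

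The cost is a slightly smaller denominator and a short text change. It would come after panel data collection: the protocol has the panel finishing its assessments in Q4 2022, and this SAP version is dated March 4, 2024. It should therefore be disclosed as a late change with its reason, which SAP Section 3 already provides for in the final report.
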